11.7.3. Amendment 2 (26 June 2023)

Rationale for Key Changes Included in Amendment 2	Affected Sections
Emerging data from Study GS-US-536-5816 suggest a higher rate of virologic rebound in participants assigned to the GS-2872 10 mg/kg group; therefore, Treatment Group 2 was removed, leading to changes in dosage information and the statistical analysis plan including sample size.	Synopsis, Study Schema, Study Procedures Table, Sections 1, 2, 3, 4, 5, 6, 8
The number of study centers increased from 50 to 55.	Synopsis
Updated the window period of the PK sampling for study drugs to ≤ 30 minutes prior to dosing of oral LEN for consistency.	Study procedures Table 1 (footnote 'o') and Section 6.3.6.1
Clarified that HIV-1 sensitivity results from screening or from the Study GS-US-536-5816 within 36 months prior to Screening Visit 2 meeting specific criteria will be considered for the inclusion in the study.	Section 4.2
Aligned the screening visit (Screening Visit 2) as per the study procedure tables for the study assessments for eligibility.	Synopsis, Sections 4.2 and 4.3
Updated the background information for GS-5423 and GS-2872 to include their synonyms 'zinlirvimab' and 'teropavimab' respectively.	Sections 1.2.2.1 and 1.2.3.1
Updated the language to clarify that the data from the DMC analysis and/or primary analysis will not be considered for the extension phase dose selection.	Synopsis, Study Schema (footnote a), Table 3 and 4 (footnote a), Sections 3.1.2, 5.3
Updated background information with respect to clinical studies of lenacapavir with GS-5423 and GS-2872.	Section 1.2.4
Clarified that the participants in Treatment Group 1 who reach Week 52 and meet criteria to enter the extension phase will receive the study regimen every 26 weeks during the extension phase.	Section 5.3, Table 3 footnote
Updated to clarify that a plasma sample from the confirmation visit will be the primary sample used for HIV-1 PR, RT, and IN genotypic and phenotypic testing.	Section 6.3.9
Minor changes to correct typographic errors, language, and to provide clarifications.	Throughout, as needed

11.7.4. Amendment 1 (18 January 2023)

Rationale for Key Changes Included in Amendment 1	Affected Sections
Instructions for management of ISRs persisting for more than 26 weeks were revised to clarify that ISRs lasting longer than 26 weeks will be followed clinically until resolution or study completion, and the time of resolution will be documented.	Section 7.7.1
Instructions for the management of ophthalmologic symptoms were added.	Section 7.7.2
Dosing and administration instructions for the handling of missed or delayed dosing were added for the cases that more than 28 weeks have passed since the last study drug dose.	Section 5.3.2
A footnote was added to clarify that participants eligible for the extension phase may opt to continue study visits beyond the last week listed under the Extension Phase column in the Study Procedures Table (Week 156), consistent with Section 3.2.	Study Procedures Table
Minor changes to correct typographic errors and clarifications.	Throughout, as needed

Table 3-6.	Analysis Visit Windows for ECG	24
Table 3-7.	Analysis Visit Window for TSH	24
Table 8-1.	Pharmacokinetic Parameters for Each Analyte	46
Table 13-1.	Study Procedures Table (Treatment Group 1).....	56
Table 13-2.	Study Procedures Table (Treatment Group 3).....	61

LIST OF ABBREVIATIONS

AE	adverse event
B/F/TAF	Bictegravir/Emtricitabine/Tenofovir Alafenamide
BIC	Bictegravir
BLQ	below the limit of quantitation
BMI	body mass index
CI	confidence interval
CK	creatinine kinase
CRF	case report form
CSR	clinical study report
DMC	data monitoring committee
ECG	Electrocardiogram
eGFR _{CG}	estimated glomerular filtration rate using Cockcroft-Gault formula
FAS	Full Analysis Set
Hb	Hemoglobin
HLT	high-level term
ITT	intent to treat
LOQ	limit of quantitation
LPLV	last patient last visit
MedDRA	Medical Dictionary for Regulatory Activities
NAb	Neutralizing antibody
PBMC	peripheral blood mononuclear cell
POC	Proof-of-Concept
PT	preferred term
PWH	people with HIV
Q1, Q3	first quartile, third quartile
SAP	statistical analysis plan
SC	subcutaneous
SD	standard deviation
SE	standard error
SOC	system organ class
SBR	Stay on baseline regimen
TAF	tenofovir alafenamide
TEAE	treatment-emergent adverse event
TFLs	tables, figures, and listings
TFV	tenofovir
TFV-DP	tenofovir diphosphate

PHARMACOKINETIC ABBREVIATIONS

λ_z	terminal elimination rate constant, estimated by linear regression of the terminal elimination phase of the log plasma/serum concentration of drug versus time curve of the drug
%AUC _{exp}	percentage of AUC extrapolated between AUC _{last} and AUC _{inf}
AUC _{inf}	area under the concentration versus time curve extrapolated to infinite time
AUC _{last}	area under the plasma/serum concentration versus time curve from time zero to the last quantifiable concentration
AUC _{0-26wk}	area under the plasma/serum concentration versus time curve from time zero to week 26
CL	clearance
C _{26wk}	Plasma/serum concentration of drug at Week 26
C _{max}	maximum observed plasma/serum concentration of drug
C _{max day1}	maximum observed plasma/serum concentration of drug at Day 1
t _{1/2}	estimate of the apparent terminal half-life of the drug in plasma/serum, calculated by dividing the natural log of 2 by the terminal elimination rate constant (λ_z)
T _{last}	time (observed time point) of last observed quantifiable plasma/serum concentration of drug
T _{max}	time (observed time point) of C _{max}
T _{max day1}	time (observed time point) of C _{max day1}
V _{ss}	volume of distribution at steady state

1. INTRODUCTION

This statistical analysis plan (SAP) describes the statistical analysis methods and data presentations to be used in tables, figures, and listings (TFLs) of Week 52 interim analysis for the Study GS-US-536-5939. The analysis will be performed when all participants have completed Week 52 visit or have prematurely discontinued from study.

This SAP is based on the study protocol amendment 3 dated 13 May 2024 and the electronic case report form (eCRF). The SAP will be finalized prior to data finalization for the Week 52 primary analysis.

1.1. Study Objectives and Endpoints

Primary Objective	Primary Endpoint

 To evaluate the efficacy of switching to a regimen of lenacapavir (LEN, Sunlenca®), GS-5423, and GS-2872 versus continuing on baseline oral antiretroviral (ARV) therapy (ART) as determined by the proportion of participants with HIV-1 RNA ≥ 50 copies/mL at Week 26 	
 Proportion of participants with HIV-1 RNA ≥ 50 copies/mL at Week 26 as determined by the United States (US) Food and Drug Administration (FDA)-defined snapshot algorithm
Secondary Objectives	Secondary Endpoints

 To evaluate the efficacy of switching to a regimen of LEN, GS-5423, and GS-2872 versus continuing on baseline oral ART as determined by the proportion of participants with HIV-1 RNA ≥ 50 copies/mL at Week 52 To evaluate the efficacy of switching to a regimen of LEN, GS-5423, and GS-2872 versus continuing on baseline oral ART as determined by the proportion of participants maintaining virologic suppression (HIV-1 RNA < 50 copies/mL) at Weeks 26 and 52 	
 Proportion of participants with HIV-1 RNA ≥ 50 copies/mL at Week 52 as determined by the US FDA-defined snapshot algorithm Proportion of participants with HIV-1 RNA < 50 copies/mL at Weeks 26 and 52 as determined by the US FDA-defined snapshot algorithm Changes from baseline in CD4+ T-cell counts at Weeks 26 and 52 Proportion of participants experiencing treatment-emergent adverse events (TEAEs)
Secondary Objectives	Secondary Endpoints

 To evaluate CD4+ T-cell counts at Weeks 26 and 52 To evaluate the safety and tolerability of the 2 treatment groups To evaluate the pharmacokinetics (PK) of GS-5423, GS-2872, and LEN To evaluate the immunogenicity of GS-5423 and GS-2872 	
 Trough concentrations at Weeks 26 and 52 and PK parameters (AUC_{0-t}, AUC_{last}, $t_{1/2}$, C_{max}, and T_{max}) for GS-5423, GS-2872, and LEN as appropriate Incidence of anti-GS-5423 and anti-GS-2872 antibodies

1.2. Study Design

This is a Phase 2, randomized, open-label, active-controlled, multicenter study to evaluate the safety and efficacy of the long-acting regimen of LEN, TAB (ie, GS-5423), and ZAB (ie, GS-2872). The study will include approximately 75 participants with sensitivity to GS-5423 and GS-2872 by protocol-defined criteria, who meet all eligibility criteria, and who will be randomized without stratification in a 2:1 ratio to Treatment Groups 1 and 3.

1.2.1. Randomized Phase

Participants in Treatment Group 1 will receive the long-acting regimen consisting of LEN, GS-5423, and GS-2872.

Participants will discontinue their baseline oral ART following administration of the complete study drugs on Day 1 (SC LEN 927 mg, oral LEN 600 mg, and IV infusions of GS-5423 and GS-2872), and will self-administer oral LEN 600 mg at home on Day 2. Participants will also receive study drug (SC LEN and IV infusion of GS-5423 and GS-2872) at Week 26.

All participants in Treatment Group 1 will return to the study center for visits at Weeks 4, 12, 24, 26, 38, 50, and 52.

Participants in Treatment Group 3 will continue their baseline oral ART through Week 52. After Day 1, participants in Treatment Group 3 will return to the study center for visits at Weeks 12, 26, 38, 50, and 52.

Duration of treatment in the Randomized Phase is 52 weeks.

1.2.2. Extension Phase

At Week 52, participants in Treatment Group 1 who receive the study drug of LEN, GS-5423, GS-2872, and complete the study through Week 52 with HIV-1 RNA < 50 copies/mL at the preceding Week 50 visit will be given the option to participate in the study extension phase. In the study extension phase, participants will continue to receive their randomized study drugs every 26 weeks.

Participants who elect not to participate or are not eligible to participate in the extension phase will resume their baseline oral ART (or appropriate regimen selected by the investigator).

Participants in Treatment Group 3 who complete the study through Week 52 with HIV-1 RNA < 50 copies/mL at the preceding Week 50 visit and in the absence of confirmed VR (as defined in protocol section 6.3.9.2.1) throughout the randomized phase of the study will be given the option to participate in the extension phase and receive the study drugs of LEN, GS-5423, and GS-2872 every 26 weeks at the dose specified for Treatment Group 1. Treatment with LEN, GS-5423, and GS-2872 will start at Week 52 and at that time the baseline oral ART will be discontinued.

Details for study procedures could be found in Section 13 (Appendix 1).

Key Eligibility Criteria

HIV-1 infected participants who meet the following criteria:

- Between 18 and 65 years of age, inclusive, at screening.
- Body weight ≥ 40 kg at Screening Visit 2.
- On stable oral ART consisting of no more than 2 drug classes (with the exception of pharmacologic boosters cobicistat or ritonavir) for ≥ 1 year prior to Screening Visit 2. A change in ART regimen ≥ 28 days prior to Screening Visit 2 for reasons other than virologic failure (VF) (eg, tolerability, simplification, drug-drug interaction profile) is allowed.
- No clinically significant documented historical resistance to the current ART regimen with the exception of isolated nucleoside reverse transcriptase inhibitor mutations including M184V or ≤ 2 thymidine analog mutations (TAMs: M41L, D67N, K70R, L210W, T215Y, and/or K219Q).
- Plasma HIV-1 RNA < 50 copies/mL at Screening Visit 2.
- Documented plasma HIV-1 RNA < 50 copies/mL for ≥ 12 months preceding Screening Visit 2 (or undetectable HIV-1 RNA level according to the local assay being used if the limit of detection is ≥ 50 copies/mL). Virologic elevations of ≥ 50 copies/mL (transient detectable viremia or “blips”) prior to screening are acceptable.
 - If HIV-1 sensitivity testing results are from > 12 months prior to screening (Inclusion Criterion 8), then documented plasma HIV-1 RNA < 50 copies/mL encompassing the time from sensitivity testing will be required.
- HIV-1 sensitivity results from screening or from the Study GS-US-536-5816 within 36 months prior to Screening Visit 2 meeting specific criteria:
 - Proviral phenotypic sensitivity to both GS-5423 and GS-2872 by the PhenoSense Assay (Monogram Biosciences). GS-5423 phenotypic sensitivity is defined as 90% inhibitory concentration (IC_{90}) ≤ 2 μ g/mL; GS-2872 phenotypic sensitivity is defined as $IC_{90} \leq 2$ μ g/mL.
- CD4+ T-cell count ≥ 200 cells/ μ L at Screening Visit 2.
- Availability of a fully active alternative ART regimen, in the opinion of the investigator, in the event of discontinuation of the current ART regimen with development of resistance.

1.3. Sample Size and Power

A sample size of 50 participants in Treatment Group 1 and 25 participants in Treatment Group 3 was chosen to estimate the proportion of participants with HIV-1 RNA ≥ 50 copies/mL at Week 26 as determined by the US FDA-defined snapshot algorithm to allow for the planning of Phase 3 studies. This study is not formally powered for treatment comparison.

Assuming no failure (0%) in Treatment Group 3 at Week 26, the number of failures in Treatment Group 1 at Week 26 would need to be ≥ 8 (16%) for the 95% CI for the difference between treatment (Treatment Group 1 versus Treatment Group 3) in the proportion of participants with HIV-1 RNA ≥ 50 copies/mL at Week 26 to exclude 0. Similarly, assuming 1 failure (4%) in Treatment Group 3 at Week 26, the number of failures in Treatment Group 1 would need to be ≥ 12 (24%) for the 95% CI for the difference between treatment (Treatment Group 1 versus Treatment Group 3) in the proportion of participants with HIV-1 RNA ≥ 50 copies/mL at Week 26 to exclude 0. The 95% CI is estimated based on an exact unconditional method {Chan 1999}.

If the underlying incidence of a specific AE is 5%, there is a 92.3% chance of observing at least 1 AE among 50 participants in Treatment Group 1 and a 72.3% chance of observing at least 1 AE among 25 participants in Treatment Group 3.

2. TYPE OF PLANNED ANALYSIS

This statistical analysis plan describes the analysis planned for the Week 52 interim analysis.

2.1. Interim Analyses

Before the final analysis, interim analyses may be conducted and the analyses may be submitted to regulatory agencies to seek guidance for the overall clinical development program and to support regulatory filings. Also, interim analyses may be used for publication and presentation at scientific meetings.

2.1.1. Week 52 Interim Analysis

[figure not shown]
In addition to the primary analysis, there will be 1 planned interim analysis – Week 52 interim analysis.

The Week 52 analysis will be conducted after all participants have completed their Week 52 visit or prematurely discontinued from study, outstanding data queries had been resolved or adjudicated as unresolvable, and the data had been cleaned and finalized for the analysis.

2.1.2. Data Monitoring Committee Analysis

An external multidisciplinary Data Monitoring Committee (DMC) will review the progress of the study and perform interim reviews of the safety data in order to protect participant welfare and preserve study integrity. To ensure the best interests of the participants, the DMC will make recommendations to the sponsor if the nature, frequency, and severity of adverse effects associated with the study treatment warrant the early termination of the study, the continuation of the study, or the continuation of the study with modifications.

There will be 1 planned DMC analysis after approximately the first 50% of participants enrolled have completed their Week 12 visit or prematurely discontinued from the study drug. Safety data will be reviewed by the DMC without formal stopping rules. CCI

In addition, if 4 or more participants in Treatment Group 1 experience confirmed VR (as defined in protocol section 6.3.9.2.1) before all participants reach Week 26, an ad hoc DMC meeting may be convened to assess the data.

A DMC meeting may be convened, and the supporting analyses conducted at other times during the study as deemed necessary. Further details will be provided in the DMC charter.

The DMC's role and responsibilities and the scope of analysis to be provided to the DMC are provided in the mutually agreed upon charter, which defines the DMC membership, meeting logistics, and meeting frequency.

2.2. Primary Analysis

The primary analysis of the primary endpoint was conducted after all participants enrolled have completed the Week 26 visit or have prematurely discontinued study drug, outstanding data queries have been resolved or adjudicated as unresolvable, and the data have been cleaned and finalized for the analysis. This analysis of the primary endpoint will serve as the final analysis for this endpoint and will be used to evaluate the efficacy of the long-acting regimen consisting of LEN, GS-5423, and GS-2872.

2.3. Final Analysis

The final analysis will be performed after all participants have completed or prematurely discontinued from the study, outstanding data queries have been resolved or adjudicated as unresolvable, and the data have been cleaned and finalized.

3. GENERAL CONSIDERATIONS FOR DATA ANALYSES

The Week 52 interim analysis will include all data collected from the randomized and the extension phases of the study. Only data collected in the randomized phase (ie, randomized phase data) will be summarized by treatment group (except that the “by-visit” summary will be up to Week 52 only), if not specified otherwise. Data collected from both phases will be included in data listings. Data included in each phase are defined as follows:

Randomized Phase Data

- For participants who do not enter the extension phase (ie, not treated in the extension phase), all available data are considered as the randomized phase data.
- For participants who enter the extension phase (ie, treated in the extension phase), randomized phase data are defined as data collected **up to** and including the first dose date of the extension phase with the exception as follows: for AEs, concomitant medications, pregnancy, and death, only data collected **prior to** the first dose date of the extension phase are included. For PK/ADA, data collected up to and including the predose timepoint on the first dose date of the extension phase is included.

Extension Phase Data

Extension phase data are only available from participants who enter the extension phase of the study. Extension phase data are defined as data collected **after** the extension phase first dose date with the exception as follows. For AEs, concomitant medications, pregnancy, and death, data collected **on or after** the extension phase first dose date are included. For PK/ADA data, data at postdose on Study Day 1 (EXT) if applicable or after Study Day 1 (EXT) is assigned to the Extension Phase.

In general, analysis results will be presented using descriptive statistics. For categorical variables, the number and percentage of participants in each category will be presented; for continuous variables, the number of participants (n), mean, standard deviation (SD) or standard error (SE), median, first quartile (Q1), third quartile (Q3), minimum, and maximum will be presented.

All statistical tests will be 2-sided and performed at the 5% significance level unless otherwise specified.

By-participant listings will be presented for all participants in the All Randomized Analysis Set and sorted by participant identification (ID) number, visit date, and time (if applicable). Data collected on log forms, such as AEs, will be presented in chronological order within the participant. The treatment group to which participants were randomized will be used in the listings. Age, sex at birth, race, and ethnicity will be included in the listings, as space permits.

3.1. Analysis Sets

Analysis sets define the participants to be included in an analysis. Analysis sets and their definitions are provided in this section. The analysis set will be identified and included as a subtitle of each table, figure, and listing.

For each analysis set, the number and percentage of participants eligible for inclusion as well as the number and percentage of participants who were excluded and the reasons for their exclusion will be summarized by treatment group.

A listing of reasons for exclusion from analysis sets will be provided by participant.

3.1.1. All Randomized Analysis Set

The All Randomized Analysis Set includes all participants who were randomized into the study. This is the primary analysis set for by-participant listings.

3.1.2. Full Analysis Set

The Full Analysis Set (FAS) includes all randomized participants who have received at least one dose of the complete long acting study drug regimen (ie, SC LEN + GS-5423 and GS-2872) or continued with their baseline ART regimen. For the FAS, all efficacy data will be included, unless specified otherwise. This is the primary analysis set for efficacy analyses.

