1.2.4. Clinical Studies of Lenacapavir With GS-5423 and GS-2872

GS-US-536-5816 is a randomized, blinded, POC Phase 1b study to evaluate the safety and efficacy of a single dose each of a long-acting regimen of LEN, GS-5423, and GS-2872 in adults with HIV-1 infection who are virologically suppressed (HIV-1 RNA < 50 copies/mL) on oral ART.

The primary cohort included eligible adults with HIV-1, no history of virologic failure (VF) or ARV drug resistance, a CD4+ T-cells nadir ≥ 350 cells/ μ L, screening CD4+ T-cells count > 500 and on first-line ART for at least 2 years with demonstrated virologic suppression (HIV-1 RNA < 50 copies/mL) for at least 18 months who had sensitivity to both GS-5423 and GS-2872, as measured by the PhenoSense monoclonal antibody assay (Monogram Biosciences), were randomized in a 1:1 ratio to 2 treatment groups.

All participants received GS-5423 (30 mg/kg intravenous [IV]) and oral LEN 600 mg Day 1 and Day 2 and LEN for subcutaneous (SC) injection 927 mg on Day 1. The 2 randomization arms differed only in the dose of GS-2872 that they received (10 mg/kg or 30 mg/kg administered IV).

Participants discontinued their background oral ARV regimen 1 day prior to receiving study drugs on Day 1. At Week 26, all participants who remained virologically suppressed, resumed their background oral ARV baseline regimen (or compatible regimen selected by the investigator) and return to the clinic for visits at Weeks 38 and 52.

Twenty-one participants were enrolled into the primary cohort and randomized, 20 received the complete study drugs (10 in each treatment group), one participant received oral LEN and withdrew consent prior to completing dosing procedures. The median age of participants was 44 years (range: 25 to 61 years), 18 (86%) were male sex at birth; and at baseline, all had HIV-1 RNA < 50 copies/mL and CD4 count ≥ 500 cells/ μ L.

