2. OBJECTIVES AND ENDPOINTS

Primary Objective	Primary Endpoint

 To evaluate the efficacy of switching to a regimen of LEN, GS-5423, and GS-2872 versus continuing on baseline oral ART as determined by the proportion of participants with HIV-1 RNA ≥ 50 copies/mL at Week 26 	
 Proportion of participants with HIV-1 RNA ≥ 50 copies/mL at Week 26 as determined by the US FDA-defined snapshot algorithm
Secondary Objectives	Secondary Endpoints

 To evaluate the efficacy of switching to a regimen of LEN, GS-5423, and GS-2872 versus continuing on baseline oral ART as determined by the proportion of participants with HIV-1 RNA ≥ 50 copies/mL at Week 52 To evaluate the efficacy of switching to a regimen of LEN, GS-5423, and GS-2872 versus continuing on baseline oral ART as determined by the proportion of participants maintaining virologic suppression (HIV-1 RNA < 50 copies/mL) at Weeks 26 and 52 To evaluate CD4+ T-cell counts at Weeks 26 and 52 To evaluate the safety and tolerability of the 2 treatment groups To evaluate the PK of GS-5423, GS-2872, and LEN To evaluate the immunogenicity of GS-5423 and GS-2872 	
 Proportion of participants with HIV-1 RNA ≥ 50 copies/mL at Week 52 as determined by the US FDA-defined snapshot algorithm Proportion of participants with HIV-1 RNA < 50 copies/mL at Weeks 26 and 52 as determined by the US FDA-defined snapshot algorithm Changes from baseline in CD4+ T-cell counts at Weeks 26 and 52 Proportion of participants experiencing TEAEs Trough concentrations at Weeks 26 and 52 and PK parameters (AUC_{0-t}, AUC_{last}, $t_{1/2}$, C_{max}, and T_{max}) for GS-5423, GS-2872, and LEN as appropriate Incidence of anti-GS-5423 and anti-GS-2872 antibodies

CCI

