5.3.1. Additional IV Infusion Instructions

GS-5423 and GS-2872 will be coadministered or administered as sequential separate IV infusions. If coadministered, the infusion of GS-5423 and GS-2872 will begin immediately following (up to 1 hour after) the last SC LEN injection. If sequentially administered, infusion of GS-5423 will begin immediately following (up to 1 hour after) the last SC LEN injection. Infusion of GS-2872 will begin at least 15 minutes following (up to 1 hour after) the completion of GS-5423 IV infusion.

Initial infusions of GS-5423 and GS-2872 will be administered over 60 minutes if coadministered as a single infusion. At subsequent coadministration dosing visits, infusions of GS-5423 and GS-2872 may be administered over ≤ 60 minutes and ≥ 30 minutes, at investigator

CCI

if sequentially administered, separate infusions of GS-5423 and GS-2872 will each be administered over 30 minutes.

Participants will remain in a monitored clinical setting for at least 30 minutes after completion of the GS-5423 and GS-2872 infusion, if coadministered, or GS-2872 infusion, if sequentially administered. Vital signs (blood pressure, pulse, and temperature) will be recorded 30 minutes (± 10 minutes) after completion of the GS-5423 and GS-2872 infusion, if coadministered, or GS-2872 infusion, if sequentially administered. If symptoms occur, the symptoms and timing of occurrence will be recorded on the electronic case report form (eCRF).

Supportive medications, including but not limited to diphenhydramine, acetaminophen, and steroids, will be available in the clinic settings during the IV infusions.

Study drug infusion will be temporarily stopped if an infusion-related adverse reaction occurs. Symptom severity will be evaluated, and supportive medications provided as clinically indicated. For mild-moderate infusion-related reactions, after symptoms have resolved, drug infusion may be resumed at half the initial rate. If the symptoms, in the judgment of the investigator, compromise the ability to continue study-specific procedures and are considered to not be in the participant's best interests, or recurrent symptoms prevent completion of infusion, the infusion will be permanently discontinued.

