8.3. Analysis Conventions

8.3.1. Analysis Sets

8.3.1.1. Efficacy

The primary analysis set for efficacy analysis is defined as the Full Analysis Set, which will include all randomized participants who have received at least 1 dose of either the complete long-acting study drug regimen (ie, SC LEN + GS-5423 + GS-2872) or baseline oral ART regimen on or after Day 1. Participants will be grouped according to the treatment to which they were randomized.

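### The Full Analysis Set admits Group 1 participants only after a complete first long-acting administration, which can raise the secondary HIV-1 RNA < 50 proportions by about 2 points per excluded participant; its ART clause also names no group.

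*SAP*

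**What the plan says.** The stated objective (protocol section 2) is "To evaluate the efficacy of switching to a regimen of LEN, GS-5423, and GS-2872 versus continuing on baseline oral ART".

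The primary efficacy set is narrower than that question. SAP section 3.1.2 takes "all randomized participants who have received at least one dose of the complete long acting study drug regimen", which it spells out as SC LEN plus both antibodies, "or continued with their baseline ART regimen". Protocol section 8.3.1.1 has a matching long-acting condition, "all randomized participants who have received at least 1 dose of either the complete long-acting study drug regimen", and on the control side asks for one dose of the "baseline oral ART regimen on or after Day 1". FAS participants are grouped as randomized (SAP section 3.2).

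The other efficacy analyses rest on the same set. The per-protocol sets are subsets of the FAS (SAP 3.1.3). The missing-equals-failure and missing-equals-excluded analyses and the subgroup analyses use the FAS (SAP 6.3.2.1 and 6.3.3). The All Randomized set serves listings (SAP 3.1.1). The Safety Analysis Set takes anyone randomized who had a dose of any study drug (SAP 3.1.4), but no efficacy table is planned on it. SAP section 3.1 does promise counts, percentages and reasons for exclusion from each set, by treatment group.

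**The concern.** On Day 1, Group 1 must take oral LEN, two SC injections and two infusions (protocol section 5.3). This sequence can break off part-way. Section 5.3.1 provides that if "recurrent symptoms prevent completion of infusion, the infusion will be permanently discontinued". In the Phase 1b primary cohort "one participant received oral LEN and withdrew consent prior to completing dosing procedures" (protocol section 1.2.4). Such a participant has been randomized and exposed and counts for safety, but appears to drop out of the efficacy set. Controls are already on ART, so their condition filters out almost nobody. Treatment is not blinded, so the filter acts after both sides know the assignment.

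Under the SAP's own snapshot (section 6.1.2), a person who stops for an adverse event or another reason, with a last value below 50 and nothing in the window, is classed as having no virologic data. That category counts against the < 50 endpoint. Removing the person from the denominator removes that outcome from Group 1. What is then estimated is suppression among people who completed the first administration, not suppression among people assigned to switch who began dosing.

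**Working it through.** **1. The plan's own figures.** The sample-size section gives the number of Group 1 failures out of 50 at which the 95% CI for the difference excludes 0: 8 with 0/25 control failures and 12 with 1/25. I inverted two one-sided 0.025 tests on the score statistic, maximised over the nuisance parameter, as in the SAP Appendix 3 code.

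- 7/50 v 0/25: -2.7% to 26.7%; 8/50 v 0/25: 0.1% to 29.1%.
- 11/50 v 1/25: -1.0% to 32.8%; 12/50 v 1/25: 0.1% to 35.0%.

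Both thresholds reproduce, so the intervals below use the planned method.

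**2. Inputs.** Planned sizes are 50 and 25 (SAP 1.3). Protocol section 1.4.1.2 reports 1 Group 1 participant at >= 50 at Week 26 and 3 at Week 52, with none among controls, and gives no denominators. The number k of Group 1 participants excluded from the FAS is not given; I take 0 to 5. I assume that 50 were randomized and began dosing, that everyone else has window data, and that the k excluded would be classed as no virologic data.

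**3. Effect on the < 50 endpoints.** With f failures:

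- FAS proportion = (50 - k - f)/(50 - k)
- any-dose proportion = (50 - k - f)/50
- gap = FAS proportion x k/50, so about 2 points per excluded participant

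| k | Wk 26 FAS | Wk 26 any dose | Gap | Wk 52 FAS | Wk 52 any dose | Gap |
|---|---|---|---|---|---|---|
| 0 | 49/50 = 98.0% | 49/50 = 98.0% | 0.0 | 47/50 = 94.0% | 47/50 = 94.0% | 0.0 |
| 1 | 48/49 = 98.0% | 48/50 = 96.0% | 2.0 | 46/49 = 93.9% | 46/50 = 92.0% | 1.9 |
| 2 | 47/48 = 97.9% | 47/50 = 94.0% | 3.9 | 45/48 = 93.8% | 45/50 = 90.0% | 3.8 |
| 3 | 46/47 = 97.9% | 46/50 = 92.0% | 5.9 | 44/47 = 93.6% | 44/50 = 88.0% | 5.6 |
| 5 | 44/45 = 97.8% | 44/50 = 88.0% | 9.8 | 42/45 = 93.3% | 42/50 = 84.0% | 9.3 |

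At k = 2, Week 26, against 25/25 suppressed controls, the difference is -2.1% (-11.7 to 12.3) on the FAS and -6.0% (-16.9 to 8.4) on the wider set.

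**4. Effect on the primary >= 50 endpoint.** At k = 2 the FAS gives 1/48 = 2.1%, difference CI -12.3% to 11.7%. The wider set gives 1/50 = 2.0%, CI -12.3% to 11.1%. The FAS figure is marginally worse for Group 1. Only if both excluded people were counted as >= 50 would the wider set be higher: 3/50 = 6.0%, CI -8.4% to 16.9%.

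**5. How large might k be?** The only guide is Phase 1b. In the primary cohort 1 of 21 was incompletely dosed (exact 95% CI 0.1% to 23.8%). That rate gives 50/21 = 2.4 expected exclusions and a chance of at least one of 1 - (20/21)^50 = 91%. Carrying the interval through, that chance runs from about 6% to over 99%. Adding the pilot cohort, all 11 of whom had the complete regimen, gives 1/32: 50/32 = 1.6 expected and 1 - (31/32)^50 = 80%. This is illustration, not an estimate for this trial.

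**6. The wording.** Group 1 stops ART only once Day 1 dosing is complete (protocol 5.3 and 6.2). An incompletely dosed Group 1 participant may therefore still be on ART. The SAP clause "or continued with their baseline ART regimen" is not tied to a group, so that person could literally qualify for the FAS and be analysed as Group 1. Two programmers could build different sets.

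**The case against.** A reader might infer that failed switches leave the denominator. The documents do not support that: one complete administration keeps a participant in the FAS whatever follows, whether rebound, discontinuation or no Week 26 dose. Only incomplete first administrations are at issue.

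A reader might also infer that the primary endpoint is flattered. It is not: it moves trivially, and against the new regimen. Many excluded participants at >= 50 would be needed to reverse this, which is unlikely to be common when ART is meant to continue until dosing is complete.

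Nor do the documents show that exclusions are driven by intolerance. The one precedent is a consent withdrawal with no reaction stated. Neither Phase 1b cohort had an adverse event leading to discontinuation, and the single infusion reaction was mild and resolved untreated. Section 5.3.1 shows the route exists, not that anyone has taken it. It would also be wrong to say that controls face no condition; the protocol asks for an ART dose on or after Day 1, though this is easy to meet.

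It can further be said that exclusions will be tabulated with reasons, that a reader can add k back by hand, and that the study is for estimation without formal power. These points stand as mitigation. They still leave no planned efficacy estimate or interval that includes the people concerned.

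Finally, redefining the primary set now is hard to defend: SAP section 2.2 says the Week 26 analysis has been done, and protocol section 1.4.1.2 already reports results. I accept that, and the fix leaves the FAS alone.

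**Conclusion.** The point holds in limited form. FAS membership in Group 1 is conditional on a post-randomization event with no comparable filter in the control arm, and the definition can be read in two ways. On the evident reading, the secondary < 50 proportions at Weeks 26 and 52 favour Group 1 by about 2 percentage points per excluded participant out of 50, or 3.9 points at Week 26 with 2 excluded. The primary >= 50 proportion is essentially unaffected.

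This rests on the planned 50 per group as the denominator, on complete window data for everyone else, and on excluded participants being classed as no virologic data. It does not establish that suppression has been overstated in this trial, though a reader might take it so: the number excluded is not given, and with none excluded the bias is nil. It is a cheap improvement, not a threat to the main result.

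**What to change.** 1. In SAP section 3.1.2 (and protocol section 8.3.1.1 at the next amendment), state that the baseline ART clause applies to Treatment Group 3 only.
2. Keep the FAS as the primary efficacy set.
3. Add supportive Week 26 and Week 52 snapshot tables, for both >= 50 and < 50, on all randomized participants given at least 1 dose of any study drug. Group them as randomized, because SAP section 3.2 would otherwise group the Safety Analysis Set by treatment received.
4. State a rule for Group 1 participants without a complete administration. The existing snapshot cannot be applied to them directly: its on-treatment cutoff and discontinuation date (SAP section 6 and Appendix 2) are anchored on the last complete long-acting dose or an ART restart, and they may have neither. For analysis, treat them as discontinued on Day 1 with their recorded reason and the baseline value as the last on-treatment value. As a bound, repeat with all of them counted as >= 50.
5. If nobody was excluded, one sentence in the report saying so replaces the extra tables.

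The cost is a wording change and one extra table run on existing data. The Group 1 < 50 proportion in the supportive table may be slightly less favourable. People randomized but never dosed would still be outside this set; SAP section 4.1 already reports their number.
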